The patient returns for screening one week after her last cycle of chemotherapy due to suspected bitter phantogeusia. The patient's bitter phantogeusia is determined by directly asking about bitter taste perception ("Did you notice an increased bitter taste during the course of chemotherapy?") and subsequently classifying the increased perception as "mild," "moderate," or "severe." If the patient rates her heightened perception of bitterness as "moderate" or "severe," meets all inclusion and exclusion criteria, and consents to the study by signing the patient information form, she is eligible for inclusion in the study. As part of the screening examination, the threshold for bitter perception and the bitter perception triggered by 500 ppm caffeine are recorded. Body composition is also measured using the BOD POD® and a weight check is performed. Quality of life is assessed using the EORTC-QLQ-30 Ovar and OV-28, and dietary intake is assessed using a 24-hour recall questionnaire (GloboDiet). In addition, perception of the other four basic tastes (sweet, sour, salty, umami) is determined using a sensory test. Furthermore, the patient is given a detailed explanation of the necessary follow-up visits required as part of the study and is handed a diary.

Visit 2

The patient returns for a follow-up visit three weeks after the end of her last course of chemotherapy. A test is conducted to assess bitterness perception of 500 ppm caffeine and to determine the bitterness perception threshold, as well as a sensory test to assess perception of the taste qualities sweet, sour, salty, and umami, a quality-of-life assessment using the EORTC-QLQ-30 Ovar and OV-28, and a dietary intake assessment using the 24-hour recall questionnaire (GloboDiet).

Visit 3

The patient returns 12 weeks after the end of her last chemotherapy session for a final examination. A test of bitterness perception using 500 ppm caffeine and determination of the bitterness perception threshold is performed, along with a sensory test to assess perception of the taste qualities sweet, sour, salty, and umami, a measurement of body composition using the BOD POD®, and a weight check. Quality of life is assessed using the EORTC-QLQ-30 Ovar and OV-28, and dietary intake is assessed using a 24-hour recall questionnaire (GloboDiet). The diary is discussed and collected.

RCT: Overview of Study Visits

	CRF	QoL (EORTC 30 and OV-28)	Medication dispense/return	Sensory test	BOP POD	Weight	Diary	24-hour recall

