V1 (1 week after CHT)	X	X	X	X	X	X	X	X
V 2 (2 weeks after V1)	X	X	X	X			X	X
V3 (12 weeks after V1)	X	X	X	X	X	X	X	X

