4.1.4. End of Participation

The patient has completed the study if she has attended all study visits. Study visits must be attended within ± 3 days of the respective appointment. The patient must have taken the prescribed study medication during the specified period. The patient must return the remaining sachets containing the powder at the final examination. All further follow-up visits after the end of the study are conducted, as mentioned above, according to an established follow-up after gynaecologic cancer treatment at the Medical University of Vienna.

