4.3. Study Medication

4.3.1. Production and Storage:

To prepare the study medication, 30 mg of homoeriodictyol sodium is granulated with food coloring, a opacifier, and a carrier material (manufactured by Symrise AG, Holzminden, Germany) and packaged in airtight bags. The powder are portioned and packed into the bags at the Institute of Physiological Chemistry using portioning spoons. The number of bags containing the portioned powder required for each study participant is collected in cardboard boxes, which are labelled for each patient according to the randomization (sequential numbers from 1 to 32). This labelling is performed by a staff member of the Institute of Physiological Chemistry who will have no contact with the study participants. The process is carried out in accordance with internationally established standards and standard operating procedures (SOPs).

The study medication is stored in the cold room (4–6°C) of the Institute of Physiological Chemistry until it is dispensed. For this purpose, the boxes labelled according to randomization are kept in a sealed aluminium box. After the study medication is dispensed to the patient, the cardboard box containing the entire medication is stored in the patient's refrigerator.

The study participants dissolve the powder in 20 ml of water immediately before use. The placebo consists of the same formulation of powder, except that the HED is replaced by a carrier substance, which the study participants also dissolve in 20 ml of water.

4.3.2. Blinding:

The study medication, both the verum and the placebo, is packaged in cardboard boxes and labelled according to randomisation.

4.3.3. Randomisation:

Randomisation is done online using the randomisation programme of the Medical University of Vienna (<https://www.meduniwien.ac.at/randomizer/web/login.php>). Patients are randomised in a 1:1 ratio without further stratification and without blocks. Randomisation of the patient takes place after the informed consent has been signed, the inclusion and exclusion criteria have been checked, the taste test has been carried out, and the impaired bitter perception has been objectively assessed (recording of the threshold for bitter perception and the bitter perception triggered by 500 ppm caffeine). If impaired bitter perception cannot be verified, the patient is documented as a 'screening failure' and excluded from the study. For further details, see 'Statistical section: Randomisation'.

4.3.4. Dosage:

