The efficacy of the treatment is defined as a reduction in the perception of bitterness by more than 30% in the treatment group compared to the placebo group. The primary endpoint will be evaluated using a paired t-test.

This will be evaluated in two analyses:

- Intention-to-treat analysis: Inclusion of all patients who used the mouthwash at least once
- Per-protocol analysis: Inclusion of patients who completed the study according to the study protocol

Secondary endpoints are also analysed using intention-to-treat and per-protocol analyses. The collected clinical and pathological data are presented descriptively using absolute values or, depending on the normality of the distribution, using the median (interquartile range) or mean (standard deviation). Metric variables are compared using Student's t-test or the Mann-Whitney U test, depending on normal distribution. Categorical variables are compared using the chi-square test and, if feasible given the number of groups, presented including the odds ratio (95% confidence interval). The study will investigate predictive factors for response to the intervention. These analyses are performed using a multivariate binary logistic regression model. The following variables are included: patient age, number of chemotherapy cycles, patient BMI, bowel resection during the primary surgery, peripheral polyneuropathy during chemotherapy, nausea at the time of study enrolment, and diarrhoea at the time of study enrolment. Version 21.0 of the statistical software SPSS (SPSS, Inc.) is used for the statistical analysis.

Patient data is pseudonymized, documented, and analysed in accordance with current data protection regulations and is not disclosed to third parties. The data is published in anonymized and aggregated form.

C) Ethical and Legal Section

1. Ethical Aspects

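### The per-protocol set for the week-3 primary endpoint is defined by 12 weeks of conduct, and no sachet count or rinse record shows use before Visit 2

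*Combined protocol and SAP*

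**What the plan says.** The document is the combined protocol and SAP; the point concerns the RCT.

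- **Endpoint timing.** Sections 3.3 and 4.1.5 place the primary comparison at week 1 and week 3. The overview table in 4.1.1 puts Visit 2 two weeks after Visit 1.
- **Analysis sets.** Section B.3 (Statistical Analysis) defines per-protocol as "Inclusion of patients who completed the study according to the study protocol" and intention-to-treat as "Inclusion of all patients who used the mouthwash at least once". Both apply to the primary endpoint.
- **Completion.** Section 4.1.4 counts a patient as having completed when she has attended all visits, each within 3 days of its date. It adds: "The patient must have taken the prescribed study medication during the specified period". Section 4.3.4 has the mouthwash used three times a day for the whole 12-week period.
- **Returns.** Section 4.1.4 states: "The patient must return the remaining sachets containing the powder at the final examination". Sections 4.1.2 and 4.3.4 also require return on withdrawal or when the mouthwash is discontinued.
- **Visit 2.** The overview table has a column "Medication dispense/return", ticked at Visits 1, 2 and 3. The Visit 2 paragraph lists the tests but does not mention medication.
- **Supply.** Under 4.3.1, after dispensing, "the cardboard box containing the entire medication is stored in" the patient's refrigerator.
- **Records.** Section 4.1.6 gives the diary side effects, other adverse events and other medications. No rinse log, sachet count or numerical adherence threshold appears anywhere.

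**The concern.** A per-protocol analysis of the week-3 endpoint should describe patients who used the product up to week 3. As B.3 and 4.1.4 read together, membership depends on 12 weeks of attendance and use, and most of that lies after the endpoint.

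This matters in two ways. First, conduct after Visit 2 may depend on what the patient noticed up to Visit 2. A patient with no benefit may stop, and so may one whose taste has recovered. Selecting on that conduct can move the week-3 contrast in either direction, and the documents do not allow the direction to be predicted. Second, the information that should decide membership, namely use between Visits 1 and 2, is not recorded in any way the plan describes. It cannot be reconstructed at week 12, because leftover sachets show how many were missed but not when.

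What is at stake is the interpretation of the primary per-protocol result, not the validity of the trial.

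**Working it through.** The plan gives no adherence figure to reproduce, so the check counts scheduled rinses and then sizes the consequences.

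**Inputs.** Three rinses a day for 12 weeks (4.3.4). Visit 2 two weeks and Visit 3 twelve weeks after Visit 1 (table in 4.1.1). 16 patients per arm, 20% dropout, 30% effect, SD 10%, 1% significance level (B.1). Assumptions: rinsing starts on the day of Visit 1, and the test is two-sided, since B.1 does not state sidedness.

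**1. Share of rinses before the endpoint**
- Before Visit 2: 3 × 14 = 42.
- Whole period: 3 × 84 = 252.
- Before Visit 2: 42/252 = 16.7%. After: 210/252 = 83.3%.
- The Visit 3 paragraph counts 12 weeks from the end of chemotherapy, which is 11 weeks after Visit 1. On that reading the total is 3 × 77 = 231, and (231 − 42)/231 = 81.8% falls after Visit 2. The two timings need reconciling, but the result hardly changes.

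**2. What a 12-week total can show**
- Full use to Visit 2, none afterwards: 42/252 = 17%. She was fully exposed for the primary endpoint, yet fails the 12-week rule.
- No use to Visit 2, full use afterwards: 210/252 = 83%. She was unexposed for the primary endpoint. Her 42 leftover sachets show a shortfall, but the same 42 would remain if she had skipped the last two weeks.

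**3. How many patients this could touch**
- Planned dropout is 0.20 × 16 = 3.2 per arm, leaving 12.8, about 13.
- Section 4.1.2 defines withdrawal as leaving before Visit 3. Up to about 3 of 16 per arm could therefore have complete week-3 data and still be outside the primary per-protocol set. The plan does not say how dropout divides before and after Visit 2.

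**4. Unrecognised non-use (illustration only)**
- Suppose k of an assumed 13 HED patients had not rinsed before Visit 2, had no effect, and went undetected. The expected effect is 30 × (1 − k/13): 27.7% for k = 1 and 25.4% for k = 2.
- B.3 sets efficacy at a reduction of more than 30%, so a shift of 2 to 5 points would affect how a per-protocol estimate near that mark is read.

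**5. Power**
- With 20% of the HED arm unexposed, the mean difference is 30 × 0.8 = 24. The HED-arm SD is √(100 + 0.2 × 0.8 × 900) = 15.6, and the pooled SD is √((100 + 244)/2) = 13.1.
- A two-sample t-test at two-sided 1% then has power 0.99 with 16 per arm and 0.96 with 13 per arm. Both exceed the planned 90%.

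**The case against.** The best defence is that the plan already covers this. The table ticks medication handling at Visit 2. Study medication appears in none of the RCT visit paragraphs, including Visit 1, where it must be dispensed, so silence at Visit 2 is no contradiction. Medication must also come back on withdrawal or discontinuation, so a declared stop would be known. Section 4.1.4 requires that the medication was taken, and 4.1.3 lets the investigator exclude for demonstrable non-compliance.

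Much of this stands, and it rules out three stronger readings that a reader might infer.

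- *Sachets come back only at the final visit.* Section 4.1.4 does not say only, and the table and the other return rules point the other way.
- *A patient who had not rinsed by Visit 2 may count as per-protocol.* The written rule bars her. The weakness lies in verifying it. To call her adherent at 83% would need a cut-off at or below that level, and the plan has none.
- *The trial loses its power.* On the plan's own figures it does not. The intention-to-treat set requires only one use of the mouthwash, so graded adherence does not affect it.

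Two things remain. The defence does not touch the mismatch in time: a 12-week rule governs a two-week endpoint. And a tick in a column that covers both dispensing and return, ticked alike at Visit 1 when nothing can yet come back, does not establish a count. A requirement to have taken the medication, or to exclude demonstrable non-compliance, needs data, and none is specified for the period before Visit 2.

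**Conclusion.** The point holds as a cheap improvement of low severity. The primary per-protocol set is selected largely on conduct after the endpoint: 83% of scheduled rinses (82% on the shorter timing) fall after Visit 2, and a patient fully adherent to Visit 2 who then stops or misses Visit 3 is excluded. No written procedure shows use before Visit 2.

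This rests on reading completion in B.3 through 4.1.4, and the specified period as the 12 weeks of 4.3.4. B.3 does not cite 4.1.4, but no other definition of completion is given. The number of patients affected and the direction of any bias are unknown; the dilution figures illustrate and do not predict.

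**What to change.** 1. Reconcile the overview table and Visit 2 paragraph in 4.1.1 with 4.1.4 and 4.3.1. State that remaining sachets are counted at Visit 2, either brought along or reported by the patient, and that the count is entered in the CRF. Repeat the count at Visit 3.
2. In B.3, define the per-protocol set by endpoint: attendance and sachet use from Visit 1 to Visit 2 for the week-3 primary endpoint, and from Visit 1 to Visit 3 for the week-12 endpoints.
3. Fix the adherence cut-off in writing before unblinding.

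The cost is one count and one CRF line at an existing visit, plus a protocol amendment. The patient must bring or report on a box kept refrigerated, and a reported count is less reliable than one made by staff. Sample size, visits and the intention-to-treat analysis stay as they are.

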4.1.5. Evaluation of efficacy

This is done by testing the perception of bitterness triggered by 500 ppm of caffeine in week 1 and week 3.

4.1.6. Monitoring of side effects and adverse events

Side effects are documented in the patient's diary, and the patient uses a visual analog scale (VAS) to rate the severity of each side effect. Other adverse events and the use of other medications are also recorded in the patient's diary.

4.2. Patients

Pilot Study

Inclusion Criteria

- 1) Patients (>18 years) with histologically confirmed gynaecological malignancy
- 2) Planned chemotherapy
- 3) Written informed consent
- 4) Expected patient compliance

Exclusion criteria:

- 1) Vomiting (CTCAE 4.03) > Grade 2 (3–5 episodes within 24 hours)
- 2) Nasogastric tube or PEG tube
- 3) Previous platinum-based chemotherapy
- 4) Conditions that impair taste perception (e.g., infections in the oral cavity)

Number of study participants:

A total of 40 patients will be enrolled in the study.

RCT

Inclusion criteria:

- 1) Patients (>18 years) with histologically confirmed ovarian cancer/tubal cancer/peritoneal cancer
- 2) Age 18–70 years
- 3) Non-smoker for at least 12 months
- 4) Completed chemotherapy with platinum and taxane
- 5) Written informed consent
- 6) Phantogeusia confirmed through patient interview
- 7) Expected patient compliance

Exclusion criteria:

- 1) Planned or ongoing treatment with a PARP inhibitor
- 2) Known intolerance to HED
- 3) Nausea and vomiting (CTCAE 4.03) > Grade 2 (3–5 episodes within 24 hours)
- 4) Nasogastric tube or PEG tube
- 5) Progressive tumour disease during adjuvant chemotherapy
- 6) Conditions that interfere with taste perception (e.g., infections in the oral cavity)
- 7) General taste disturbance verified by baseline tests

Number of study patients:

A total of 32 patients will be enrolled in the study (active treatment group: 16 patients, placebo group: 16 patients).

4.3. Study Medication

4.3.1. Production and Storage:

To prepare the study medication, 30 mg of homoeriodictyol sodium is granulated with food coloring, a opacifier, and a carrier material (manufactured by Symrise AG, Holzminden, Germany) and packaged in airtight bags. The powder are portioned and packed into the bags at the Institute of Physiological Chemistry using portioning spoons. The number of bags containing the portioned powder required for each study participant is collected in cardboard boxes, which are labelled for each patient according to the randomization (sequential numbers from 1 to 32). This labelling is performed by a staff member of the Institute of Physiological Chemistry who will have no contact with the study participants. The process is carried out in accordance with internationally established standards and standard operating procedures (SOPs).

The study medication is stored in the cold room (4–6°C) of the Institute of Physiological Chemistry until it is dispensed. For this purpose, the boxes labelled according to randomization are kept in a sealed aluminium box. After the study medication is dispensed to the patient, the cardboard box containing the entire medication is stored in the patient's refrigerator.

The study participants dissolve the powder in 20 ml of water immediately before use. The placebo consists of the same formulation of powder, except that the HED is replaced by a carrier substance, which the study participants also dissolve in 20 ml of water.

4.3.2. Blinding:

The study medication, both the verum and the placebo, is packaged in cardboard boxes and labelled according to randomisation.

4.3.3. Randomisation:

Randomisation is done online using the randomisation programme of the Medical University of Vienna (<https://www.meduniwien.ac.at/randomizer/web/login.php>). Patients are randomised in a 1:1 ratio without further stratification and without blocks. Randomisation of the patient takes place after the informed consent has been signed, the inclusion and exclusion criteria have been checked, the taste test has been carried out, and the impaired bitter perception has been objectively assessed (recording of the threshold for bitter perception and the bitter perception triggered by 500 ppm caffeine). If impaired bitter perception cannot be verified, the patient is documented as a 'screening failure' and excluded from the study. For further details, see 'Statistical section: Randomisation'.

4.3.4. Dosage:

The 20 ml mouthwash solution (depending on randomisation, either water containing 30 mg HED, food colouring, a opacifier and a carrier, or just water containing food colouring, a

opacifier and a carrier as a placebo) is administered three times daily before each main meal throughout the entire 12-week study period. The patient may discontinue treatment at any time if side effects occur, but must report this immediately to the study team. Should the patient discontinue the mouthwash, the study medications must be returned.

4.4. Experimental design and schedule

4.4.1. Investigation of the perception of bitter taste

In ovarian cancer patients with chemotherapy-induced bitter phantogeusia, the perception of bitterness from caffeine is tested. To this purpose, study participants are administered 20 ml of an aqueous mouthwash solution containing 500 ppm caffeine. After rinsing and spitting out the caffeine solution, the patients rate the bitterness of the solution on a scale from 0 (slightly bitter) to 10 (very bitter). The perception of bitterness is then tested in the presence of HED by administering a 500 ppm caffeine rinse solution with 100 ppm HED added. After rinsing and spitting out this caffeine-HED solution, the patients again rate the bitterness on a scale of 0 to 10. The perception of bitterness of caffeine alone and of caffeine after HED is used for comparison between groups and visits. In addition, a threshold test for bitter taste is carried out to determine the concentration of caffeine at which the patients perceive a bitter taste. To determine this, the patients taste mouthwash solutions one after the other, starting with water, at increasing concentrations of caffeine. Patients indicate the concentration at which they first detect a taste (detection threshold) and the concentration at which they can recognize a specific taste (recognition threshold), and whether the taste intensifies from one concentration to the next. The resulting threshold value for bitter perception is also used for comparison between groups and visits.

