4.5. Timeline

Pilot study

Recruitment	Months 1–12
Analysis	Months 12–15
Total	15 months

RCT

Study planning	Months 1–6
Recruitment	Months 7–30
Analysis	Months 30–36
Total	36 months

B) Statistical Section

1. Sample Size

Forty patients will be recruited for the pilot study. This study is intended to provide a descriptive analysis of taste changes during chemotherapy and to validate the tests used for the double-blind, randomized, placebo-controlled study planned afterwards. The double-blind, randomized, placebo-controlled study will include 32 female patients. Based on current studies [3], the prevalence of bitter phantogeusia is approximately 30–78%. An HED mouthwash leads to a 30% reduction in bitter perception (standard deviation 10%) [7], which describes the expected effect size. The primary endpoint is defined as “comparison of the bitter perception triggered by 500 ppm caffeine from week 1 to week 3 between the study group (HED mouthwash) and the control group (water mouthwash).” The patient rates bitterness perception on a continuous scale from 0 to 10. The study endpoint is therefore a continuous variable. The data from week 1 and week 3 will be analysed using a paired t-test to compare the intervention group with the control group. Taking into account a 20% dropout rate, a 90% power level, and a significance level of 1%, this results in a sample size of 32 patients. These will be randomized 1:1, resulting in a group size of 16 patients each. Approximately 77% of patients experience bitter phantosmia following platinum-based combination chemotherapy. Therefore, approximately 40 patients will need to be screened.

2. Randomization

Randomization is performed online using the randomization program of the Medical University of Vienna (<https://www.meduniwien.ac.at/randomizer/web/login.php>). The complete randomization list is provided to [name], MSc, a staff member of the Institute of Physiological Chemistry. Study medication is packaged and coded, with coding performed exclusively by [name]. The coded, randomized study medication is then distributed as needed to the investigators, who administer the study medication to the patients. The investigators and the statistician may not view the randomization list until the study has been completed.

3. Statistical Analysis

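### The primary 0-10 bitterness rating has no point for 'not bitter', so the more-than-30% efficacy criterion depends on an arbitrary zero and overstates the true reduction

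*Combined protocol and SAP*

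**What the plan says.** The primary endpoint of the RCT is the rated bitterness of 500 ppm caffeine, week 1 to week 3, compared between groups (sections 3.3 and 4.1.5). Section 4.4.1 gives the only definition of the rating: "the patients rate the bitterness of the solution on a scale from 0 (slightly bitter) to 10 (very bitter". The same 0-10 rating is used for caffeine with HED added.

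Part B, section 1 (Sample Size) repeats the range without labels: "The patient rates bitterness perception on a continuous scale from 0 to 10". It therefore neither confirms nor corrects the lower label.

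Two statements then treat the rating as something of which a percentage can be taken:

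- Planning assumption (Part B, section 1): "An HED mouthwash leads to a 30% reduction in bitter perception (standard deviation 10%) [7], which describes the expected effect size".
- Efficacy definition (Part B, section 3): "reduction in the perception of bitterness by more than 30% in the treatment group compared to the placebo group".

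The threshold test in section 4.4.1 starts from water, but its result is a caffeine concentration. It supplies no zero for the 500 ppm rating.

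**The concern.** A percentage reduction has a fixed meaning only when the zero of the scale means none of the quantity. Here zero is labelled as a positive sensation. Two things follow.

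- The percentage depends on how much bitterness the lower label stands for, which may differ between patients and is not stated. Taking the label at its word, the baseline in the denominator is too small and the recorded percentage is too large.
- A patient who tastes no bitterness and one who tastes slight bitterness both score 0, so a change from slight to none cannot be recorded.

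At stake is the plan's own definition of success. It could be met by a true reduction smaller than the one it names. It is also unclear whether a 30% effect with SD 10%, taken from reference 7, means the same thing on this scale.

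**Working it through.** **Inputs.** From the documents: the scale labels (4.4.1); the 30% reduction with SD 10%, 1% significance, 90% power, 20% dropout, 32 patients in two groups of 16 (Part B, section 1); the criterion of more than 30% (Part B, section 3). Assumed, because the documents give no value: the position *c* of 'slightly bitter' on a true scale where 0 is no bitterness and 10 is very bitter; even use of the scale between the labels; and, for step 4 only, a true baseline with mean 5 and SD 1.5.

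**1. The plan's own figure.** If the 30% and 10% are in the same units, the standardised effect is 30/10 = 3.0. An exact two-sample t-test at 1% with 90% power then needs 5 (one-sided) or 6 (two-sided) per arm. Dividing by 0.8 gives 6.25 and 7.5, so 7 or 8 per arm and 14 or 16 in total. The stated 32 is not reproduced. That is a separate question and is not evidence for this point. It matters here only because, on the plan's inputs, power with 12 or 13 completers per arm exceeds 99.99%.

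**2. What a recorded 30% means.** Let *T* be true intensity and *R* the recorded score:

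R = 10(T − c)/(10 − c), so T = c + R(10 − c)/10.

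For a recorded fall from 5.0 to 3.5, which is 1.5/5.0 = 30%:

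| c (assumed) | True start | True end | True reduction |
|---|---|---|---|
| 0 | 5.0 | 3.5 | 30% |
| 1 | 1 + 0.9 × 5.0 = 5.5 | 1 + 0.9 × 3.5 = 4.15 | 1.35/5.5 = 24.5% |
| 2 | 2 + 0.8 × 5.0 = 6.0 | 2 + 0.8 × 3.5 = 4.8 | 1.2/6.0 = 20% |

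Simply adding *c* to each score gives 1.5/6 = 25% and 1.5/7 = 21%. That version lets the scale run past 10, but the answer hardly changes.

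**3. The other direction.** Above the floor, recorded % = true % × T/(T − c), where *T* is the true baseline. A recorded 30% is therefore reached by a true reduction of 30% × (T − c)/T.

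| c (assumed) | True 30% from T = 5 is recorded as | True 30% from T = 8 is recorded as | True reduction that records as 30% from T = 5 |
|---|---|---|---|
| 0.5 | 33.3% | 32.0% | 27% |
| 1 | 37.5% | 34.3% | 24% |
| 2 | 50% | 40% | 18% |
| 3 | 75% | 48% | 12% |

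The overstatement is larger at lower baselines, so it also varies with case mix.

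**4. Effect on the test.** In points, R₀ − R₁ = 10(T₀ − T₁)/(10 − c). The origin drops out, and the common multiplier cancels in a t statistic. Only flooring at 0 can cost power. This was checked by simulation (20,000 trials per row): a two-sample t-test on change, two-sided 1%, 13 per arm (16 × 0.8 = 12.8), true reduction 30% with SD 10% under HED and 0% with SD 10% under placebo.

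| c (assumed) | Power | Recorded mean reduction, HED | HED patients scoring 0 at week 3 |
|---|---|---|---|
| 0 | 99.98% | 30% | 0% |
| 1 | 99.98% | 37% | 1% |
| 2 | 99.9% | 49% | 9% |
| 3 | 98.6% | 64% | 35% |

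The recorded percentage moves a great deal while the power hardly moves.

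**The case against.** A reader might infer several stronger things from the label. The documents do not support them.

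- **That the power of the trial is undermined.** It is not, to any extent that matters. Part B describes a t-test on a continuous 0-10 rating, and step 4 shows that a test on changes in points does not depend on the origin. Simulated power stays at 98.6% or more.
- **That the primary outcome is censored where benefit should appear.** This goes too far. The plan expects a partial reduction (about 40% in section 2.1, 30% in Part B), not abolition. RCT Visit 1 requires self-rated moderate or severe bitterness, and section 4.3.3 requires impaired bitter perception to be verified, although neither sets a minimum 500 ppm score. Flooring is appreciable only for the larger assumed offsets.
- **That the 30% figure cannot hold on this scale.** The scale behind reference 7 is not in the documents. If it carried the same labels, the figure would transfer directly. What can be said is that the plan does not show that it transfers.
- **That the endpoint is undefined when a baseline score is 0.** That is true only of an individual's percentage change. The criterion is worded for groups, and no per-patient percentage is specified for the primary test.

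It can also be said that the label may be a slip of wording or translation, that the rating form itself is not in the documents, and that some patients may use 0 for none whatever the label says. All of this is possible, but nothing in the documents shows it. If it is a slip, correcting it costs nothing. If patients differ in how they read 0, the origin differs between them, which is the same problem.

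**Conclusion.** The point holds, with a limited reach. The only definition of the primary rating gives no score for absence of bitterness, while efficacy is defined by a percentage of that rating. If 'slightly bitter' lies anywhere above none and the scale is used evenly, recorded percentages overstate true ones, and the more-than-30% criterion can be met by less: about 24.5% or 20% for a recorded fall from 5.0 to 3.5 with the label 1 or 2 points above none. The direction follows from the label. The size rests entirely on the assumed offset.

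Two things are affected: the efficacy criterion, and the step that carries 30% (SD 10%) from an undescribed source scale to this one. The comparison of changes in points is not materially affected, and this point by itself gives no reason to change the sample size. The inability to separate none from slight bitterness is real, but how often it would occur is unknown.

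**What to change.** 1. In section 4.4.1 and on the rating form, label 0 as 'not bitter at all' and keep 10 as 'very bitter'. Use the same labels in Part B, section 1, for the caffeine-with-HED rating, and wherever the pilot uses this rating. The pilot visits in section 4.1.1 describe an intensity test without stating its scale.
2. Restate the efficacy criterion in Part B, section 3, either as a between-group difference in scale points or as a group-level percentage on the re-anchored scale, with the formula written out. It needs a replacement; removing the percentage alone would leave success undefined.
3. In Part B, section 1, state the scale on which the 30% and the SD of 10% were measured and what they correspond to in points here.

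The cost is wording in the protocol and on the form. The downside is that any ratings already taken with 0 labelled 'slightly bitter' would not be directly comparable with later ones. The documents do not say whether any have been taken. If so, they should be reported separately.
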